#### 1608 **4.5 Specimen collection procedures**

##### 1609 *4.5.1 Timing and volume of blood draw*

1610 All participants will have a blood samples collected at four time-points and urine samples at two  
1611 time-points (if not already available as part of routine clinical care). Blood will be obtained by  
1612 venipuncture, or from an existing venous or arterial catheter. Urine will be collected via clean catch  
1613 urine or via catheter.  
1614

##### 1615 Specimen Collection Time Points

- 1616 1. T1=0 hrs (just before study drug administration)
  - 1617 2. T2=24 hrs (+/- 2 hrs)
  - 1618 3. T3=72 hrs (+/- 2 hrs)
  - 1619 4. T4=120hrs (+/- 12hrs)
- 1620

##### 1621 *4.5.2 Specimen samples*

1622 At the T1, T2, T3, and T4 time points, blood will be sent for complete blood count (including  
1623 hemoglobin, white blood cell count, platelet count), a serum chemistry (including sodium,  
1624 potassium, chloride, bicarbonate, blood urea nitrogen, creatinine, glucose, aspartate transaminase,  
1625 alanine transaminase, and total bilirubin), and a venous blood gas to measure lactate. These tests  
1626 will be performed by the clinical laboratory at each site. As many of these laboratory tests are  
1627 commonly obtained for clinical purposes, these tests do not need to be repeated if a result is  
1628 available from the clinical care of the participant within 2 hours of the time point (or within 12 hours  
1629 of the T4 time-point).  
1630

1631 In addition to traditional clinical markers, 25ml of blood will be obtained for future biomarker analysis  
1632 (including inflammatory biomarkers, markers of endothelial function, and markers of mitochondrial  
1633 function), and measurement of vitamin C, vitamin B1, and cortisol levels. Levels of vitamin C,  
1634 vitamin B1, and cortisol will be measured at time T1 and time T3 only. 20ml of urine will be collected  
1635 for future biomarker analysis at T1, T2, and T3.  
1636

1637 If performed as part of standard-of-care, results of urinalysis and urine sediment testing will be  
1638 collected prior to enrollment.  
1639

##### 1640 *4.5.3 Biomarker tube initial processing and shipping*

[figure not shown]
1641 Please see accompanying blood collection standard operating procedure for full details. In brief,  
1642 15ml of blood will be drawn into EDTA tubes and 10ml of blood will be drawn into a corvac tube.  
1643 From one of the EDTA tubes, 3ml of whole blood will be initially drawn and separated into 3x 1ml  
1644 aliquots. Plasma will then be isolated from the EDTA tube(s) and aliquoted into cryovials as follows:  
1645 2x 1ml aliquots and the remainder in 0.5ml aliquots. Serum will then be isolated from the corvac  
1646 tube, and separated into 1ml aliquots. Cryovials will be protected from light and frozen at -80°C until  
1647 processing. An additional 20ml of urine will also be collected, centrifuged, and separated into 1ml  
1648 aliquots then frozen at -80°C until processing.  
1649

1650 Sites will be expected to ship frozen samples to the coordinating center after every 5 enrollments.  
1651 The coordinating center will assist with all shipping procedures.

1652

#### 1653 4.6 Study flow diagram

1654

1655

1656

#### 1657 4.7 General Sepsis Management

1658 Investigators should follow local sepsis management guidelines. No specific sepsis bundle is  
1659 required by this study, however the early administration of antibiotics, maintenance of a mean  
1660 arterial pressure  $\geq 65$ mmHg with a combination of volume resuscitation and vasopressors, and early  
1661 source control are recommended—as detailed in the Surviving Sepsis Guidelines. Elements of  
1662 sepsis care should be reported on the online case report form (CRF).

1663

#### 1664 4.8 Glucometer use during the study period

1665 High dose vitamin C has been shown to falsely elevate glucose level readings when measured with  
1666 certain point-of-care glucometers employing glucosedehydrogenase-pyrroloquinoline quinone  
1667 amperometric methods. Some commonly used glucometer brands using this approach include  
1668 Accu-Chek (Roche Diagnostic) and Optium (Abbott Diabetes Care) (but not StatStrip; Nova  
1669 Biomedical). While the effects of high-dose vitamin C on glucometer readings have been seen  
1670 primarily at higher doses of vitamin C than are intended for use in this trial, we recommend that  
1671 sites explore what glucometers are in use in local ICUs. If locally used glucometers may be  
1672 impacted by high serum concentrations of vitamin C (as determined by the manufacturer), we  
1673 recommend that clinical teams caring for enrolled participants be alerted to the possibility of falsely  
1674 elevated blood-glucose levels when measured by glucometer. If there is a clinical concern about a  
1675 glucose reading obtained via glucometer, a serum glucose should be obtained which will not be  
1676 impacted by vitamin C. In the event of an emergency related to suspected hypoglycemia, glucose  
1677 should be immediately given while a serum glucose level is pending.

1678

### 1679 5. OUTCOMES

#### 1680 5.1 Definitions

##### 1681 5.1.1 Primary Outcome

1682 The primary outcome will be the absolute change in the Sequential Organ Failure Assessment  
1683 (SOFA) score from enrollment (time=0) to 72 hours after drug administration. The SOFA score will  
1684 be defined using a modification in which the SaO2/FiO2 ratio is substituted for the PaO2/FiO2 ratio

1685 as has been previously described. This modified score will be used so that participants without an  
 1686 existing arterial catheter can be spared arterial puncture.  
 1687

Points	SaO 2 */FiO 2 §	Blood Pressure	GCS 	Bilirubin (mg/dL)	Creatinine (mg/dL)	Platelets (x10  µL)
1	<512	< 70 mm/Hg	13–14	1.2–1.9	1.2 – 1.9	<150
2	<357	dopamine ≤ 5 µg/kg/min or dobutamine (any dose)	10–12	2–5.9	2.0 – 3.4	<100
3	<214	dopamine > 5µg/kg/min, epinephrine/norepinephrine ≤ 0.1 µg/kg/min	6–9	6–11.9	3.5 – 4.9 Or UOP † <500ml/day	<50
4	<89	dopamine > 15, epinephrine/norepinephrine > 0.1 µg/kg/min	<6	>12	> 5.0 UOP † <200ml/day	<20

1688 \*SaO2=Oxygen saturation (%); § = Fraction of inspired oxygen (%); || = Glasgow Coma Scale; † = Urine Output  
 1689

1690 **5.1.2 Key Secondary Outcomes**

1691 Incidence of Acute Renal Failure – Renal failure will be defined as the development of Kidney  
 1692 Disease Improving Global Outcomes [KDIGO] Stage 3 acute kidney injury during the index ICU stay  
 1693 after study enrollment.  
 1694

KDIGO Stage	Serum creatinine criteria	Urine output criteria
1	Increase in serum creatinine of more than or equal to 0.3 mg/dl (≥ 26.4 µmol/l) or increase to more than or equal to 150% to 200% (1.5- to 2-fold) from baseline	Less than 0.5 ml/kg per hour for more than 6 hours
2	Increase in serum creatinine to more than 200% to 300% (> 2- to 3-fold) from baseline	Less than 0.5 ml/kg per hour for more than 12 hours
3	Increase in serum creatinine to more than 300% (> 3-fold) from baseline (or serum creatinine of more than or equal to 4.0 mg/dl [≥ 354 µmol/l] with an acute increase of at least 0.5 mg/dl [44 µmol/l])	Less than 0.3 ml/kg per hour for 24 hours or anuria for 12 hours OR New renal replacement therapy (RRT)

1695  
 1696 30-Day Mortality – Mortality at 30-days. This will be assessed by review of the medical records if the  
 1697 participant remains in the hospital or if the participant expired while in the hospital. If the participant  
 1698 was discharged, 30-day mortality will be assessed by contacting the participant by phone or by  
 1699 searching the National Center for Health Statistics (NCHS) National Death Index (NDI) consistent  
 1700 with a recent multicenter phase III trial in sepsis. Phone calls will be made by the research team at  
 1701 each site.  
 1702

1703 **5.2 Rationale for Outcomes**

1704 **Change in SOFA score:** Organ failure is highly associated with mortality and improvement in  
 1705 organ function is a key goal for critical care physicians. In the study by Marik et al., participants  
 1706 who received the 3-drug regimen had substantial improvements in the trajectory of organ failure  
 1707 over the first 72-hours of their ICU stay. If the combination of vitamin C, hydrocortisone, and vitamin  
 1708 B1 can improve organ function in the first 72-hours following ICU admission, we believe that  
 1709 clinicians will likely quickly adopt this safe and inexpensive therapy. Importantly, this outcome can  
 1710 be measured early in the hospital stay and is therefore less likely to be affected by other potential  
 1711 elements of hospital care that can affect more distal outcomes (e.g., mortality).

1712  
1713  
1714  
1715  
1716  
1717  
1718  
1719  
1720  
1721  
1722  
1723  
1724  
1725  
1726  
1727  
1728  
1729  
1730  
1731  
1732  
1733  
1734  
1735  
1736  
1737  
1738  
1739  
1740  
1741  
1742  
1743  
1744  
1745  
1746  
1747  
1748  
1749  
1750  
1751  
1752  
1753  
1754  
1755  
1756  
1757  
1758  
1759  
1760  
1761

**Kidney Injury:** Renal failure has been estimated to occur in 23% of participants with sepsis and over 50% of participants with septic shock. In studies of participants with septic shock, there is a step-wise increase in mortality with worsening acute kidney injury (AKI). In addition, many participants who experience renal injury during septic shock do not recover renal function prior to hospital discharge and may require long term dialysis. As both data from the study by Marik et. al. and a separate study of vitamin B1 in septic shock have shown substantial improvements in renal outcomes, kidney failure is a natural secondary outcome and one that could change practice independently from other factors – in other words, many clinicians would likely provide this therapy if they knew that kidney function could be protected, since this organ is vital to long-term health.

**Mortality:** Finally, we will measure 30-day mortality. We anticipate that the combination of vitamin C, hydrocortisone, and vitamin B1 will reduce mortality in this high-risk population.

### **5.3 Additional Secondary Outcomes**

#### *5.3.1 Additional secondary outcomes*

Additional secondary outcomes will include length of ICU stay, length of hospital stay, ventilator-free days over the first 7-days after enrollment, shock-free days over the first 7-days after enrollment, and the incidence of delirium on day #3 of the ICU stay (as assessed using the Confusion Assessment Method [CAM-ICU] system). Sites at which the CAM-ICU is performed daily as part of standard-of-care should assess whether delirium occurs on any day during the initial ICU stay. See Appendix #2.

#### *5.3.2 90-day follow-up for Quality of Life assessment*

Sites may choose to participate in a long-term outcomes substudy exploring the effects of ascorbic acid, hydrocortisone, and thiamine vs. placebo on quality of life following sepsis. If a site chooses to participate, a trained research assistant/investigator at the site (who is blinded to treatment arm) will contact all participants who were alive at 30-days, and perform the SF-36 at day 90 following enrollment. The SF-36 is a 36-Item Short-Form Health Survey (SF-36), a validated survey of general quality of life in adults, can be administered in person or over the telephone by research personnel. It measures eight different dimensions: physical functioning, bodily pain, role limitations due to physical health problems, role limitations due to personal or emotional problems, emotional well-being, social functioning, energy/fatigue, and general health perceptions, as well as one question asking about perceived changes in health. The telephone version of the 36-Item Short-Form Health Survey has been validated and used in sepsis.

### **5.4 Safety**

#### *5.4.1 Definitions*

The following definitions will be used:

Adverse event: any untoward medical occurrence in a participant to whom a medicinal product is administered and which does not necessarily have a causal relationship with this treatment

Serious adverse event: any untoward medical occurrence that at any dose requires inpatient hospitalization or prolongation of existing hospitalization, results in persistent or significant disability or incapacity, results in a congenital anomaly or birth defect, is life-threatening, or results in death

Unexpected serious adverse event: a serious adverse reaction, the nature, severity or outcome of which is not consistent with the reference safety information

1762 **5.4.2 Specific adverse event data collection**

1763 To assess specific and potentially serious adverse events that may be related to the combination of  
 1764 the study medications, we will collect data on the following:  
 1765

Serious Adverse Event	Definition
Hyperglycemia	Serum glucose >300mg/dl in the first 120-hours after enrollment
Hypernatremia	Serum sodium (> 150 mmol/L) occurring in the first 120-hours after enrollment
New Infection	As determined by the site principal investigator at each site. Should be a new organism or site of infection and believed to be unrelated to the initial presenting infectious source. Many will have the initiation of new antibiotics or a change in antibiotics.
Catheter-site	
Lung	
Gastrointestinal	
Urinary tract	
Other	
Serious allergic reaction	Anaphylaxis or other allergic reaction requiring systemic corticosteroids. Allergic reaction should be related (or suspected to be related) to the study medication
Renal calculus	Development of a renal calculus between enrollment and 30-day follow-up (based on question asked during follow-up phone call).

1766

1767 **5.4.3 Adverse Event Reporting**

1768 Any Unexpected Serious Adverse Events thought to be related to the study drug (as determined by  
 1769 the site investigator) will be reported to the and all above listed Serious Adverse Events will be  
 1770 reported to the coordinating site, the data safety monitoring board (see below), and the regulatory  
 1771 authorities as applicable (i.e. IRB, FDA). Reporting of Serious Adverse Events will be done in  
 1772 aggregate after every 50 patients are enrolled. Unexpected Serious Adverse Event will additionally  
 1773 be reported to the coordinating site within 72-hours.  
 1774

1774

1775 **5.4.5 Safety Monitoring Labs**

1776 As detailed above, safety monitoring labs will be obtained at 120-hours, after completion of the  
 1777 study protocol.  
 1778

1778

1779 **6. SAMPLE SIZE CALCULATION AND STATISTICAL ANALYSIS PLAN**

1780 **6.1 Sample size calculation**

1781 The study has been powered to have at least 80% power for the primary outcome and all key  
 1782 secondary outcomes as follows:  
 1783

1783

1784 **SOFA Score:** Based on preliminary data, we conservatively anticipate a decrease in SOFA score  
 1785 of 6 (standard deviation [SD]: 4) in the treatment group and 4 (SD: 2) in the placebo group. With  
 1786 these estimates, enrollment of **200 participants (100/arm)** at an alpha of 0.05 and using a t-test  
 1787 with unequal variance, the trial will provide > 99% power to detect a statistical significant difference  
 1788 between groups.  
 1789

1789

1790 **Kidney Injury:** Based on preliminary data from our study of vitamin B1 in septic shock, we  
 1791 anticipate that 30% of participants in the treatment group and 55% in the placebo group will have  
 1792 renal failure which will result in a 94% power for this outcome. This calculation and following  
 1793 calculation were performed using the Fisher's exact test.  
 1794

1794

1795 **Mortality:** Based on preliminary data, we anticipate that the control group will have a mortality  
 1796 of 40%. We estimate a treatment effect of 50% (risk ratio: 0.50) resulting in a mortality of 20% in the  
 1797 treatment group. With these estimates, 182 participants will lead to 80% power. To further increase  
 1798 the trial's power and due to potential loss-to-follow-up, we will aim to enroll 200 participants. These

1799 estimates are conservative compared to the Marik et al. study which found a treatment effect  
1800 corresponding to a risk ratio of 0.21 which persisted in adjusted analysis.  
1801

## 1802 **6.2 Statistical analysis plan**

### 1803 *6.2.1 General considerations*

1804 The statistical analyses and reporting will adhere to the CONSORT guidelines. All tests will be  
1805 two-sided, a p-value < 0.05 will be considered significant, and all confidence intervals will have 95%  
1806 coverage. All analyses will be conducted on a modified intention-to-treat basis only including  
1807 participants receiving at least the first dose of the study medications. In a double-blind trial, this  
1808 approach is unbiased while increasing precision. The two groups will be compared in relation to  
1809 baseline characteristics using descriptive statistics.  
1810

1811 The persons conducting the statistical analysis will be blinded to the randomized allocation. Groups  
1812 will be designated as “A” and “B” until all pre-specified analyses are performed and shared with all  
1813 authors and the Data Safety Monitoring Board.  
1814

### 1815 *6.2.2 SOFA score and renal failure*

1816 The change in SOFA score will be calculated and compared between groups using the Wilcoxon  
1817 Rank Sum test (if the change is not normally distributed) or by a t-test if the change is approximately  
1818 normally distributed. Fisher’s exact tests will be used to compare the incidence of renal failure  
1819 during the index ICU stay.  
1820

1821 If a participant expires prior to the 72-hour time point, SOFA scores will be imputed based on a pre-  
1822 defined plan as follows. If a participant expires before 24-hours has elapsed, a 20% increase from  
1823 baseline will be imputed. If a participant expires between 24-hours and 48-hours, a 15% increase  
1824 from the 24-hour time point will be imputed. If a participant dies between 48-hours and 72-hours, a  
1825 20% increase from the 24-hour time point will be imputed. Sensitivity analyses will be performed  
1826 using various other imputation techniques. Specifically, we will perform 1) a sensitivity analysis in  
1827 which the worst possible SOFA score (score of 24) is imputed for those participants who expire, 2) a  
1828 sensitivity analysis in which the last SOFA score for participants who expire will be carried forward,  
1829 and 3) a sensitivity analysis in which only those patients who survive to 72-hours are included.  
1830 These sensitivity analyses were chosen to model ‘worst-possible’ and ‘best-possible’ scenarios. For  
1831 the secondary outcome of renal failure, participants who expire during their ICU stay will be  
1832 assessed to have developed renal failure if they demonstrated any degree of unresolved KDIGO  
1833 acute kidney injury prior to death. If there was no evidence of acute kidney injury prior to death or if  
1834 kidney injury had fully resolved, these participants will be assessed as not having developed renal  
1835 failure.  
1836

### 1837 *6.2.3 30-day mortality*

1838 Survival until 30 days will be analyzed using survival analysis. Participants lost to follow-up will be  
1839 censored and the censoring will be assumed non-informative. Results will be presented with  
1840 Kaplan-Meier curves and the groups compared using the log-rank test. Hazard ratios with 95%  
1841 confidence intervals will be obtained using Cox’s proportional hazards models. The proportional  
1842 hazards assumption will be verified by visual inspection of the Kaplan-Meier curves and statistically  
1843 by including a product term (i.e. “interaction”) between the treatment group variable and the natural  
1844 logarithm of time in the model. If the proportional hazards assumption is not met, only the Kaplan-  
1845 Meier curves and the p-value from the log-rank test will be presented.  
1846

1847 Adverse events and other binary outcomes will be presented and analyzed like renal failure.  
1848

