### **2.2 Allocation**

Participants will be randomized in a 1:1 ratio to either the combination of vitamin C, hydrocortisone, and vitamin B1 or placebo in blocks with random sizes of 2 or 4. The randomization will be stratified according to site. An independent statistician will create the randomization list using a random number generator. The complete list will only be shared with an independent pharmacy consultant, who will not be involved in clinical care. The pharmacy consultant and the independent statistician will both store the randomization list. The research pharmacy at each enrolling site will receive a site-specific randomization list.

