## 6. SAMPLE SIZE CALCULATION AND STATISTICAL ANALYSIS PLAN

### 6.1 Sample size calculation

The study has been powered to have at least 80% power for the primary outcome and all key secondary outcomes as follows:

**SOFA Score:** Based on preliminary data, we conservatively anticipate a decrease in SOFA score of 6 (standard deviation [SD]: 4) in the treatment group and 4 (SD: 2) in the placebo group. With these estimates, enrollment of **200 participants (100/arm)** at an alpha of 0.05 and using a t-test with unequal variance, the trial will provide > 99% power to detect a statistical significant difference between groups.

**Kidney Injury:** Based on preliminary data from our study of vitamin B1 in septic shock, we anticipate that 30% of participants in the treatment group and 55% in the placebo group will have renal failure which will result in a 94% power for this outcome. This calculation and following calculation were performed using the Fisher's exact test.

**Mortality:** Based on preliminary data, we anticipate that the control group will have a mortality of 40%. We estimate a treatment effect of 50% (risk ratio: 0.50) resulting in a mortality of 20% in the treatment group. With these estimates, 182 participants will lead to 80% power. To further increase

the trial's power and due to potential loss-to-follow-up, we will aim to enroll 200 participants. These estimates are conservative compared to the Marik et al. study which found a treatment effect corresponding to a risk ratio of 0.21 which persisted in adjusted analysis.

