### 6.2.3 30-day mortality

Survival until 30 days will be analyzed using survival analysis. Participants lost to follow-up will be censored and the censoring will be assumed non-informative. Results will be presented with Kaplan-Meier curves and the groups compared using the log-rank test. Hazard ratios with 95% confidence intervals will be obtained using Cox's proportional hazards models. The proportional hazards assumption will be verified by visual inspection of the Kaplan-Meier curves and statistically by including a product term (i.e. "interaction") between the treatment group variable and the natural logarithm of time in the model. If the proportional hazards assumption is not met, only the Kaplan-Meier curves and the p-value from the log-rank test will be presented.

Adverse events and other binary outcomes will be presented and analyzed like renal failure.

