## 671 **6.2 Statistical analysis plan**

### 672 *6.2.1 General considerations*

673 The statistical analyses and reporting will adhere to the CONSORT guidelines. All tests will be  
674 two-sided, a p-value < 0.05 will be considered significant, and all confidence intervals will have 95%  
675 coverage. All analyses will be conducted on a modified intention-to-treat basis only including  
676 participants receiving at least the first dose of the study medications. In a double-blind trial, this  
677 approach is unbiased while increasing precision. The two groups will be compared in relation to  
678 baseline characteristics using descriptive statistics.

679

680 The persons conducting the statistical analysis will be blinded to the randomized allocation. Groups  
681 will be designated as “A” and “B” until all pre-specified analyses are performed and shared with all  
682 authors and the Data Safety Monitoring Board.

683

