#### 1859 *6.2.5 Subgroup analyses*

1860 The analysis will include three pre-defined subgroup analyses for the primary and key secondary  
1861 outcomes according to 1) participants with initially high SOFA scores ( $\geq 9$ ). This cut-off was chosen  
1862 to represent a population with a  $\geq 50\%$  predicted likelihood of mortality 2) baseline vitamin B1  
1863 deficiency and 3) baseline adrenal insufficiency. We will not plan to perform a subgroup analysis  
1864 according to vitamin C deficiency, as prior work has shown that the vast majority of participants with  
1865 septic shock have vitamin C levels below the reference range. Vitamin B1 deficiency will be  
1866 defined as a plasma vitamin B1 level  $\leq 7$  nmol/L as has been previously described. Adrenal  
1867 insufficiency will be defined as a cortisol level  $< 10\mu\text{g/dL}$ . The trial is not powered to detect  
1868 subgroup differences and these will be considered exploratory and hypothesis generating.  
1869

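### The 30-day mortality analysis adjusts for nothing, although baseline SOFA is collected and treated as prognostic; a modest amount of power is given up

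*SAP*

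**What the plan says.** Protocol section 6.2.3 states: "Results will be presented with Kaplan-Meier curves and the groups compared using the log-rank test". Hazard ratios come from Cox models. Neither the test nor the model has a named covariate or stratum. The SAP document prints section 6.2.3 twice, once for each protocol version it contains, and both carry the same text, including "Kaplan-Meier curves and the groups compared using the log-rank test". If proportional hazards fails, only the curves and the log-rank p-value are to be reported.

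Section 6.2.1 sets two-sided 5% tests. It gives no general rule on adjustment and uses baseline characteristics descriptively only.

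Four other places bear on this:

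- Section 2.2: "The randomization will be stratified according to site", in blocks of 2 or 4.
- Section 5.1.1: the SOFA score at enrollment is one half of the primary outcome.
- Section 5.2 ties organ failure closely to death. Section 6.2.5 singles out "participants with initially high SOFA scores", with a cut-off of 9 meant to mark a predicted mortality of 50% or more. That is used for an exploratory subgroup analysis, which does cover mortality.
- Section 6.1: "We estimate a treatment effect of 50% (risk ratio: 0.50) resulting in a mortality of 20% in the treatment group", and "With these estimates, 182 participants will lead to 80% power". Enrollment is set at 200.

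**The concern.** In a proportional hazards model, leaving out a covariate that predicts death pulls the treatment hazard ratio toward 1 even when the arms are perfectly balanced on it, and power falls with it. Omission also leaves any chance difference in baseline severity in the comparison. The plan names such a covariate, collects it before treatment and does not use it to adjust mortality.

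Two things are at stake. One is power on a key secondary outcome that the plan cares enough about to allow a sample size increase (section 6.1, sample size adjustment). The other is pre-specification: if the SAP is silent, any SOFA-adjusted mortality result produced later is post hoc and open to dispute.

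**Working it through.** **1. The plan's own figure.** Inputs from sections 6.1 and 6.2.1: 40% versus 20%, two-sided 0.05, 80% power, Fisher's exact test. The two-proportion formula gives 82 per arm without continuity correction and 91 with it, so 2 × 91 = 182. Exact enumeration of Fisher's test at 91 per arm gives 80.8% power. The stated figure reproduces.

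**2. Power of the test actually planned.** The sizing used Fisher's test, but the analysis is a log-rank test. Under proportional hazards, HR = ln(0.8)/ln(0.6) = 0.437. With 200 participants, expected deaths are 100 × 0.40 + 100 × 0.20 = 60. Schoenfeld: (√60 / 2) × |ln 0.437| − 1.96 = 3.873 × 0.828 − 1.96 = 1.25, which is 89.4% power. Fisher's test at 100 per arm gives 84.4%.

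**3. How prognostic SOFA might be.** The documents give only the cut-off. Suppose a fraction q of the cohort has SOFA of 9 or more with 50% mortality, and mortality is 40% overall. The rest then have (0.40 − 0.50q)/(1 − q). For q = 0.5 that is 30%, and the log hazard ratio between halves is ln[ln(0.5)/ln(0.7)] = 0.66. The two halves of a normal score lie about 1.6 SD apart, so this is 0.66/1.6 ≈ 0.42 per SD. The upper value of 0.70 is an assumption with no source in the documents.

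**4. Simulation at 40% versus 20%.** 200 participants, 13 uneven sites, 1:1 within site in blocks of 2 or 4, exponential times censored at 30 days, no loss to follow-up, marginal mortality held fixed. 1,000 runs per row, Monte Carlo error about 1 point. Power in %:

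| SOFA log HR per SD | Site SD (log hazard) | Log-rank | Site-stratified log-rank | Cox + SOFA | Cox + SOFA, site strata |
|---|---|---|---|---|---|
| 0 | 0 | 89.2 | 88.8 | 88.2 | 87.7 |
| 0 | 0.4 | 89.4 | 89.3 | 89.3 | 89.4 |
| 0.4 | 0 | 87.1 | 85.9 | 86.9 | 85.5 |
| 0.4 | 0.4 | 88.4 | 88.6 | 90.2 | 89.8 |
| 0.7 | 0 | 88.2 | 86.9 | 92.5 | 92.0 |
| 0.7 | 0.4 | 88.5 | 88.5 | 92.1 | 92.2 |
| 1.0 | 0 | 88.0 | 87.2 | 96.5 | 94.9 |
| 1.0 | 0.4 | 88.5 | 88.5 | 96.3 | 95.1 |

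With SOFA entered only as 9 or more versus less, at q = 0.5, 0.6 and 0.7 (3,000 runs each), power is 88.2, 89.5 and 90.1% adjusted against 87.5, 88.4 and 88.3% unadjusted.

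**5. Both effect sizes.** Over log HR 0.42 to 0.70 per SD, power is 87-89% unadjusted and 88-93% with SOFA at 40% versus 20%. At 40% versus 25%, an effect not in the documents, it is 62-64% and 65-72%.

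**6. Where the gain comes from.** At log HR 0.7 with no site variation, the mean treatment log HR moves from −0.835 (SE 0.278) to −0.915 (SE 0.280). The ratio goes from 0.835/0.278 = 3.00 to 0.915/0.280 = 3.27. Over all scenarios the mean SE is 0.277-0.280 unadjusted, 0.278-0.284 with SOFA and 0.281-0.298 with SOFA and site strata. It does not shrink.

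**7. Chance imbalance.** With 100 per arm, the difference in mean baseline SOFA has SE √(2/100) = 0.14 SD. A 2-SE imbalance (0.28 SD) shifts the unadjusted log HR by 0.28 × 0.42 = 0.12 to 0.28 × 0.70 = 0.20. That is a factor of e^0.12 = 1.13 to e^0.20 = 1.22 on the hazard ratio, against a treatment SE of about 0.28.

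**8. Validity.** Under no effect (40% in both arms, 2,500 runs in each of three scenarios), the unstratified log-rank test rejected in 4.3-5.3% and Cox with SOFA in 3.9-5.2%.

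**The case against.** The best defense is that a marginal, assumption-light log-rank test is a legitimate choice for a key secondary outcome, that it is valid, and that it already exceeds the plan's 80% goal at the planned effect. At the plan's own SOFA cut-off, adjustment gains only about 1-2 points. The larger gains need a stronger SOFA effect, or the 40% versus 25% scenario, and neither is in the documents. All of that stands and limits the size of the point. It does not remove the point: the covariate is already collected, a halving of mortality is an optimistic effect, and imbalance and post hoc adjustment matter apart from power.

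Three stronger readings are tempting but are not supported:

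- *That precision is lost.* The standard error of the log hazard ratio does not fall with adjustment. What changes is the target, from a marginal to a conditional hazard ratio.
- *That ignoring the site strata costs power or validity.* A site-stratified log-rank test changed power by −1.3 to +0.2 points, and site strata on top of SOFA by about −2.5 to +1.5. Type I error of the unstratified test was not inflated. With about 13 competitively enrolling sites and about 60 deaths, the strata are thin.
- *That the plan ignores SOFA for mortality.* Section 6.2.5 pre-specifies a subgroup analysis by SOFA. It is not adjustment, but it is use.

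Two practical objections also stand. Section 6.2.3 deliberately keeps the log-rank p-value when proportional hazards fails, and a Cox-based main test must not lose that. Baseline SOFA may also be incomplete, and no rule covers that; participants with known vital status could then drop out of an adjusted model.

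**Conclusion.** The point holds as a modest, nearly costless improvement, not as an error in the planned test. Over an assumed SOFA effect of 0.42 to 0.70 log HR per SD, adjusting for baseline SOFA adds about 0-4 points of power at 40% versus 20% and about 3-8 points at 40% versus 25%. It also corrects chance imbalance that could move the hazard ratio by 13-22% at 2 SE.

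The result rests on the SOFA effect, the share of participants at 9 or more, the between-site variation, the site sizes and exponential survival without loss to follow-up. None of these is in the documents. If SOFA were not prognostic in this cohort, adjustment would gain nothing and cost at most about a point. That no adjustment is intended is inferred from silence in sections 6.2.1 and 6.2.3, but it is the natural reading.

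**What to change.** In section 6.2.3:

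1. Make the main mortality estimate and test a Cox model with treatment and continuous baseline (T1) SOFA, and label the hazard ratio as conditional on SOFA.
2. Add a simple rule for missing baseline SOFA components, applied without regard to arm, so that no participant with known vital status is dropped.
3. State whether site enters. It may be a stratum to reflect the randomization, with small sites pooled by a rule fixed before unblinding, but no power gain should be claimed for it.
4. Keep the Kaplan-Meier curves and the unadjusted log-rank test as supportive results, and keep the log-rank p-value as the result if proportional hazards fails. Fix the criterion for that in advance, since it decides which p-value counts.

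The cost is SAP wording only; site and baseline SOFA are already collected. The downsides are that the hazard ratio becomes conditional and is not directly comparable with an unadjusted one, and that site strata can cost about 1-2 points of power if sites do not differ.
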